8 STUDY ENROLLMENT/EVALUATIONS

8.1 Patient Screening and Enrollment

Consecutive patients who potentially meet the study inclusion and exclusion criteria will be screened for eligibility. Diagnostic imaging studies to confirm the diagnosis of AIS with a Lenke type 1 or type 2 curve must be completed within 90 days of the planned date of surgery. If, at an interim point following the initial imaging, and prior to surgery, the subject experiences a significant change in his/her clinical presentation, the changes should be documented and the images repeated. Patients will be screened as follows:

- Consecutive patients are potentially eligible for entry into the study based on their age and whether their medical condition appears to generally fit the characteristics specific to this study.
- After the study is explained and questions are answered to the satisfaction of the prospective study participant, the patient being invited to participate in the study indicates their consent by signing the consent form (or a separate assent form, if required by your IRB/EC.) Any patient under the age of 18 being invited to participate in the study indicates their verbal assent, and their parent/guardian signs the consent form.
- *If required by your institution and/or IRB/EC:* If the child reaches the age of majority during the course of the study, consent to continue (re-consent) must be obtained using the current, approved consent form prior to any further study-specific procedures or assessments.
- A patient is considered enrolled in the study after signing the IRB/EC approved informed consent. Consented patients complete the remainder of the screening process to confirm study eligibility. Patients who do not fulfill the screening criteria are considered Screening Failures and will be documented on the Screening & Enrollment Log. Screening failures will not count against the total number of subjects eligible for analysis.
- Subjects who have signed (or had a parent/guardian sign) the informed consent and fulfilled the Inclusion/Exclusion criteria are then scheduled for surgery. It is important that surgery be scheduled within 90 days from the dates of the required pre-operative x-rays and within 90 days from the date that the subject completed the required pre-operative questionnaires for the study.

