8.10 Subject Withdrawal

Subjects have the right to withdraw their consent at any time during the study. If a subject requests to withdraw from the study, all information regarding the subject's withdrawal and disposition must be recorded in the subject's medical record. A Study Exit case report form, including a full description of the circumstances related to the withdrawal, must be completed.

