9.2 Adverse Event Reporting

Any AE that occurs during the subject's participation in the study will be recorded on the Adverse Event case report form. Pre-existing medical conditions or symptoms occurring prior to the initiation of the study will not be reported as AEs but a worsening of a pre-existing medical condition or symptom will be reported as an AE. Pain, neurological status and functional impairment should be considered AEs when a subject's complaint for any of these symptoms results in an unscheduled visit or when a subject presents with new or worsening symptoms as compared to a previous visit.

All AEs will be followed until the event is resolved or considered to be stable. Relevant source documentation must be available to confirm the occurrence of an AE and must be provided to the sponsor upon request.

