11.3 Periodic Monitoring Visits

Periodic site monitoring visits will be performed during the study by a designated study monitor assigned by the Sponsor. The purposes of the visits are to confirm compliance to the protocol, review regulatory documents, accurate and complete records are being maintained and to compare source documents to completed CRFs for completeness and consistency. The initial monitoring visit to a site will be scheduled soon after the first 2 to 5 patients are enrolled in the study and may occur prior to the first surgery. The frequency of subsequent visits will be dependent upon the rate of enrollment and site performance on previous monitoring visits. If possible, monitoring visits will be performed at least annually. Specific assessments during a monitoring visit include:

- Continued site acceptability
- Compliance to the protocol
- IRB/EC approval status
- Use of the approved informed consent
- Adequacy of source documents
- Complete and accurate CRFs
- Reporting of adverse events
- Protocol deviations
- Site records

If it is determined during a monitoring visit that there are significant non-compliance issues at a site, including adherence to the protocol or applicable regulatory requirements, the issues will be discussed with the Investigator and Study Coordinator and the site will be instructed how to gain compliance. If continued non-compliance is detected on a subsequent monitoring visit, it may be necessary to terminate site participation in the study.

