12.4 Analysis Populations

Analysis Populations are defined as follows:

- The Intent-to-Treat (ITT) population includes all enrolled subjects.
- The Per-Protocol population includes all enrolled subjects who have no major protocol violations (defined as not meeting inclusion/exclusion criteria or not being consented properly).

The effectiveness analysis will be performed on the ITT population. Analysis of the per-protocol population will be confirmatory of the ITT analysis. The safety analysis will be performed on the ITT population.

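### Safety is analysed on everyone who consented and proved eligible, so subjects who never reach surgery can dilute revision, removal and device-related rates

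*Combined protocol and SAP*

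**What the plan says.** Section 12.4 defines two populations. The first reads "The Intent-to-Treat (ITT) population includes all enrolled subjects". The second, per-protocol, is the enrolled subjects without eligibility or consent violations. Neither requires that surgery took place. Safety goes to the first: "The safety analysis will be performed on the ITT population".

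Section 8.1 sets the moment of enrolment: "A patient is considered enrolled in the study after signing the IRB/EC approved informed consent". It then makes one exception: "Screening failures will not count against the total number of subjects eligible for analysis". Subjects who consented and "fulfilled the Inclusion/Exclusion criteria are then scheduled for surgery", so there is an interval between becoming an analysable subject and being operated on. Section 8.10 allows exit during that interval: "Subjects have the right to withdraw their consent at any time during the study".

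Section 12.6 plans descriptive rates of adverse events, serious adverse events, revisions and removals by follow-up interval, and names no denominator. Section 9.1.3 defines revision and removal by reference to the implanted configuration.

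**The concern.** A safety rate should be computed on subjects who could have had the event. Revision and removal presuppose an implant, and a device-related event presupposes exposure to the device. A subject who consents, is found eligible and then withdraws or is cancelled before surgery adds one to the stated denominator and nothing to these numerators.

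For efficacy, keeping all enrolled subjects is usually the cautious choice. For implant-dependent safety rates it works the other way, because it can only lower them. Adverse-event evaluation is the primary safety objective (section 5.2), and the descriptive rates in section 12.6 are its only planned summary. A dilution of this kind does not shrink as the sample grows.

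**Working it through.** **Step 1: the plan's own count.** Section 12.3 assumes a mean correction of 4.0 and SD 8.4 against a reference of 2.2, with a two-sided one-sample t-test at 0.05 and 80% power. The difference is 4.0 − 2.2 = 1.8. With the noncentral t distribution, n = 172 gives power 0.7980 and n = 173 gives 0.8003, so 173 is reproduced. Allowing for 15% attrition, 173/0.85 = 203.5, rounded up to 204. Planned losses over the whole study are 204 − 173 = 31. These figures are not in dispute; 204 is taken as the planned ITT count.

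**Step 2: who is in the denominator.** ITT is all enrolled (12.4). Enrolled means consented (8.1). Screening failures are removed (8.1). What remains is eligible subjects, operated or not. Let k be the number never operated.

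**Step 3: rates that need an implant.** If p is the rate among operated subjects and never-operated subjects contribute no events:

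rate on ITT = p × (204 − k)/204

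The documents do not give k, so the shares and the true rates below are assumptions.

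| Never operated | k | Factor | True 10% reads | True 3% reads |
|---|---|---|---|---|
| none | 0 | 1.000 | 10.0% | 3.0% |
| about 2% | 4 | 200/204 = 0.980 | 9.80% | 2.94% |
| about 5% | 10 | 194/204 = 0.951 | 9.51% | 2.85% |
| extreme bound | 31 | 173/204 = 0.848 | 8.48% | 2.54% |

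The last row puts every loss planned over 24 months before surgery. It is a ceiling, not an expectation.

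**Step 4: overall AE and SAE rates.** If never-operated subjects have recorded events at rate q:

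rate on ITT = [p × (204 − k) + q × k]/204

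This is below p only when q is below p. The documents do not settle q. Section 9.2 points to collection from consent, since any AE during a subject's "participation in the study will be recorded on the Adverse Event case report form"; the synopsis and section 5.2 also describe continuous monitoring. Section 9.1.1, however, ties an AE to a subject undergoing surgery, and sections 8.3.1 and 8.6.1 schedule AE assessment only from the operative stage. With no pre-operative collection, q = 0 and Step 3 applies.

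**Step 5: scale.** The 95% sampling half-width at n = 204 is 1.96 × √(0.10 × 0.90/204) = 4.1 points for a 10% rate and 1.96 × √(0.03 × 0.97/204) = 2.3 points for a 3% rate. Under the 2–5% assumption the shifts are 0.2 to 0.5 points and 0.06 to 0.15 points.

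**The case against.** The strongest reply is that section 12.6, the operative safety specification, reports by follow-up interval. A subject who exits before surgery has no follow-up interval. If the analyst counts subjects under follow-up, most or all of the effect disappears. This stands: interval rates are affected only if the ITT count is used. It does not remove the point, because ITT is the only population the plan assigns to safety.

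Second, operated subjects may have been meant. Section 4.2 describes the treatment group as treated patients, and the synopsis and sections 4.4 and 7.1 speak of 204 subjects with the device. That is fair evidence of intent, but none of these is an analysis population, and section 12.3 speaks of 204 enrolled.

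Third, the affected group may be very small. Some pre-operative dropouts might be classed as screening failures, although the text does not say so. Section 11.3 foresees a first monitoring visit "soon after the first 2 to 5 patients are enrolled in the study and may occur prior to the first surgery". That shows a lag between enrolment and surgery; it is not evidence of dropout.

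Two stronger readings are tempting, and the documents do not support them:

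- A reader might infer that every safety rate is biased in the device's favour. Section 9.2 can be read as capturing pre-operative events, and then the overall AE and SAE rates could move either way.
- A reader might infer that a never-operated subject cannot have a procedure-related event under any circumstances. Section 8.3 provides for antibiotics before surgery and for anaesthesia, section 9.5.1 lists anaphylaxis and anaesthesia-related events as risks, and section 9.4 rates relatedness to general surgery as well. A case cancelled after induction but before incision could produce such an event. Impossibility is secure for revision, removal and device-related events; for procedure-related events it holds very largely.

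**Conclusion.** The point holds in a limited form. The plan states a rule, rather than merely omitting a detail, that leaves eligible never-operated subjects in the safety population. Where the ITT count is the denominator, revision, removal and device-related rates are understated by the factor (204 − k)/204, and procedure-related rates very nearly so. For overall AE and SAE rates the understatement depends on whether events between consent and surgery are collected.

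The size is probably small. Under the assumed 2–5% share it is well inside sampling error, and even the extreme bound moves a 10% rate only to 8.5% and a 3% rate to 2.5%. If nobody leaves before surgery there is no effect. Safety is descriptive, with no test or planned decision attached, and nothing here touches the primary effectiveness result. Severity: minor.

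**What to change.** - In 12.4, replace ITT for safety with all subjects in whom anaesthesia for the study surgery was started, including those excluded intra-operatively. Use this population for overall and procedure-related AE and SAE rates. Anchoring on anaesthesia rather than incision keeps events in cases cancelled after induction.
- For device-related, revision and removal rates, use the subjects who received the study system. Subjects excluded intra-operatively without it cannot have a revision or removal.
- In 12.6, state the denominator at each follow-up interval.
- List events between consent and surgery separately, and report never-operated subjects with reasons in the disposition summary.
- Leave the effectiveness ITT unchanged.

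The cost is wording in 12.4 and 12.6, one listing and one disposition line. Implant-dependent and procedure-related rates would become slightly less favourable.

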12.5 Analysis of Primary Endpoint

The primary effectiveness endpoint will be evaluated by a two-sided exact test of the MESA Rail implant success rate (mean thoracic correction) against the literature reported mean thoracic correction of 2.2 degrees.

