5 STUDY OBJECTIVES/OUTCOMES

5.1 Primary Effectiveness Objective

The primary effectiveness objective is:

Restoration and maintenance of thoracic kyphosis and coronal curve correction.

- Quantitative assessment:
 - Cobb Angles – Coronal and Sagittal
 - Thoracic kyphosis as measured from the upper endplate of T4 to the lower endplate of T12
 - Lumbar lordosis as measured from the lower endplate of L1 to the upper endplate of S1

The increased stiffness of the MESA Rail is designed for the restoration and maintenance of thoracic kyphosis as well as coronal correction of deformities such as AIS after surgery. The restoration and subsequent maintenance of the thoracic kyphosis and coronal curve correction during surgery is expected to be as good as if not better than results reported for standard Ø5.5mm and Ø4.5mm CoCr pedicle screw and rod systems in these patient populations.

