8.3 Hospitalization/Surgery/Discharge

Subjects will be admitted to the hospital according to the Investigator's standard for non-cervical spine surgery. Prophylactic antibiotics may be administered prior to surgery in accordance with the surgeon's standard of care and anesthesia will be administered per standard operating procedures. The system will be implanted in accordance with methods detailed in the instructions for use for the MESA Rail Deformity System.

Data points required on the Operative case report form must be documented at the time of surgery. Intra-operative adverse events must be recorded and documented on an Adverse Event case report form.

A Subject may be excluded from the study intra-operatively at the discretion of the Investigator if unexpected findings/occurrences dictate deviation from the intended study procedure. Justification for an intra-operative exclusion and alternative surgical procedure must be fully documented in the subject's medical record and on the Study Exit case report form. A subject who is excluded intra-operatively will be considered an overall treatment failure.

If the patient experienced an adverse event(s) during the hospitalization it should be documented and recorded on an Adverse Event case report form. The subject may be instructed to return to normal activity at the discretion of the Investigator.

Additional post-operative restrictions may be imposed according to the standard of care normally utilized by the Investigator. In addition, subjects should be instructed to notify the Investigator if experiencing untoward events including but not limited to noticeable pain, numbness, tingling, or weakness that does not decrease with rest, swelling of the lower extremities that does not decrease, or increased pain, erythema, edema or drainage from the surgical incision. The Investigator should then determine if an evaluation is warranted.

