12.2 Study Hypothesis

The primary objective of this study is to evaluate the effectiveness of the MESA Rail Deformity System in terms of restoring and maintaining thoracic kyphosis in the treatment of patients with symptomatic AIS. The primary effectiveness endpoint is the rate of overall subject success (minimal loss of thoracic kyphosis) at 24 months. The primary hypothesis of this trial is that the clinical performance of the K2M MESA Rail implant is non-inferior to the clinical performance achieved and achieved with fusion utilizing a standard Ø5.5mm or Ø4.5mm CoCr rod.

A PubMed literature review was conducted to assemble relevant publications utilizing results from posterior instrumentation fusion surgeries in patients with AIS. Searches included all peer-reviewed journals published between January 2000 and March 2013. Sample sizes, patient populations, evaluated variables, results, and recorded complications were assessed for each selected article. Only data regarding thoracic kyphosis measurements of single-stage posterior fusion cases were incorporated into the thoracic kyphosis table used for statistical analysis. Articles were entirely excluded from the statistical analysis if results combined data from multi-stage cases or if data were extracted through meta-analysis.

The following table gives the preoperative thoracic kyphosis measurements as well as the thoracic kyphosis measurements collected at the last follow-up period from all relevant posterior fusion surgeries in patients with AIS:

| Thoracic Kyphosis | | | | | | | | | |
|----------------------------------|-----|-------|------|---------|------|------|------|---------------------|-------------|
| paper # | n | Preop | | Last FU | | Diff | | Mean difference x N | Std Dev x N |
| | | Mean | SD | Mean | SD | Mean | SD | | |
| 1 ¹ | 9 | 31.9 | 10.4 | 26.0 | 9.8 | 5.9 | 10.1 | 53.1 | 90.9 |
| 1 | 3 | 31.0 | 9.5 | 29.7 | 5.5 | 1.3 | 7.5 | 3.9 | 22.5 |
| 1 | 34 | 28.2 | 13.0 | 26.5 | 11.0 | 1.7 | 12.0 | 57.8 | 408.0 |
| 1 | 9 | 23.0 | 8.0 | 23.0 | 11.0 | 0.0 | 9.5 | 0.0 | 85.5 |
| 1 | 60 | 26.7 | 13.0 | 25.0 | 9.6 | 1.7 | 11.3 | 102.0 | 678.0 |
| 1 | 31 | 22.8 | 11.0 | 25.7 | 8.8 | -2.9 | 9.9 | -89.9 | 306.9 |
| 2 ² | 83 | 23.0 | 12.0 | 20.2 | 8.4 | 2.8 | 11.4 | 234.9 | 946.2 |
| 3 ³ | 111 | 29.0 | 14.0 | 23.0 | 10.8 | 6.0 | 12.2 | 666.0 | 1354.2 |
| 3 | 299 | 22.0 | 14.1 | 22.0 | 10.3 | 1.0 | 5.0 | 299.0 | 1495.0 |
| Weighted Mean Difference and SD: | | | | | | | | 2.1 | 8.4 |

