The study hypothesis is that the RAIL system is superior to other systems in Thoracic Kyphosis Correction. The hypotheses can be written:

$$\begin{aligned} H_0: \mu_R &< OPC - \delta \\ H_1: \mu_R &\geq OPC - \delta \end{aligned}$$

where μ_R is the mean Thoracic Kyphosis Correction of the RAIL system and OPC is the Objective Performance Criteria of 2.2 and $\delta = 2$ degrees.

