12.3 Sample Size

If the mean Thoracic Kyphosis Correction of the RAIL system is 4.0 with a standard deviation of 8.4, then 173 subjects provides 80% power to detect a statistically significant difference between the mean correction and the OPC of 2.2 using a two-sided one-sample t-test at a significance level of 0.05. In order to account for approximately 15% attrition, based on clinical experience, 204 subjects will be enrolled.

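### Sections 12.2 and 12.5 define and test the primary endpoint as a success rate, but the hypotheses and the 80% power are for a mean tested by a one-sample t-test

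*Combined protocol and SAP*

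**What the plan says.** Four places describe the primary analysis, and they split two against two.

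**A rate.** Section 12.2 states: "The primary effectiveness endpoint is the rate of overall subject success (minimal loss of thoracic kyphosis) at 24 months". Section 12.5, whose single sentence is the only description of the primary test, plans a "two-sided exact test of the MESA Rail implant success rate (mean thoracic correction) against the literature reported mean thoracic correction of 2.2 degrees".

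**A mean.** Later in Section 12.2, H0 and H1 are written on μ_R, which "is the mean Thoracic Kyphosis Correction of the RAIL system and OPC is the Objective Performance Criteria of 2.2", with a margin δ of 2 degrees. Section 12.3 opens its calculation with "If the mean Thoracic Kyphosis Correction of the RAIL system is 4.0 with a standard deviation of 8.4" and sizes the trial at 173 subjects for 80% power against 2.2, "using a two-sided one-sample t-test at a significance level of 0.05". Allowing for about 15% attrition, this becomes 204 enrolled.

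The measurement itself is clear. Section 5.1 lists "Thoracic kyphosis as measured from the upper endplate of T4 to the lower endplate of T12". The only rule that makes an individual subject a failure is in Section 8.3: "A subject who is excluded intra-operatively will be considered an overall treatment failure". It carries no kyphosis threshold. The 15% improvement criterion in Section 5.3.1 applies to the pain VAS only.

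**The concern.** A success rate is a proportion between 0 and 1, and 2.2 degrees is not a value it can be tested against. Testing a rate needs two further numbers: the change in degrees that separates a success from a failure, and the success rate expected with standard rods. The plan gives neither. The phrase about minimal loss in Section 12.2 has no number attached, and the literature table reports means and SDs, not responder rates.

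Taken as a test of a mean, Section 12.5 still does not name the test that was powered, because an exact test is not the one-sample t-test of Section 12.3.

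Whoever runs the analysis therefore has to choose the type of endpoint, the test and possibly a cut-off. The study has one arm and is compared with a fixed literature figure. If those choices are made once the data are visible, a reader cannot check the reported primary test against the plan.

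**Working it through.** **Inputs.** From Section 12.3: assumed mean 4.0, SD 8.4, two-sided α 0.05, 173 evaluable, 15% attrition. From Sections 12.2, 12.3 and 12.5: benchmark 2.2. Distance: 4.0 − 2.2 = 1.8 degrees.

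**Step 1. The plan's own figure.** For a one-sample t-test the power comes from the noncentral t distribution with n − 1 degrees of freedom and noncentrality (1.8/8.4)·√n. At n = 173 the noncentrality is 0.2143 × 13.153 = 2.82.

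- n = 172 gives 79.80%, and n = 173 gives 80.03%. So 173 is the smallest n that reaches 80%.
- Normal approximation as a cross-check: (8.4 × (1.960 + 0.842)/1.8)² ≈ 171.
- Attrition: 173/0.85 = 203.5, rounded up to 204.

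The plan's figures are reproduced for the t-test of a mean.

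**Step 2. Reading 12.5 as an exact or rank test of location against 2.2.** Simulated with normal data, distance 1.8, SD 8.4, n = 173:

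- Wilcoxon signed-rank test, 20,000 runs: 78.6%.
- Sign-flip permutation test, which is an exact test of a mean if the distribution is symmetric, 2,000 runs: about 79% (Monte Carlo error about 1 point).

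The loss against 80.03% is one to two points.

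**Step 3. Reading 12.5 as a test of a rate.** The documents do not allow a power calculation, so this is an illustration under stated assumptions. The outcome is normal with SD 8.4, its mean is 2.2 under the null and 4.0 under the alternative, and a subject succeeds if the value is at or above a cut-off c. This follows the direction of Section 12.3, where larger is the hoped-for result. Then p0 = 1 − Φ((c − 2.2)/8.4) and p1 = 1 − Φ((c − 4.0)/8.4). The test is an equal-tailed exact binomial test at two-sided 0.05.

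| Assumed cut-off c (degrees) | p0 | p1 | Power at n = 173 | n for 80% |
|---|---|---|---|---|
| −5 | 80.4% | 85.8% | 42% | 415 |
| 0 | 60.3% | 68.3% | 55% | 303 |
| 2.2 | 50.0% | 58.5% | 60% | 289 |
| 5 | 36.9% | 45.3% | 61% | 294 |
| 10 | 17.7% | 23.8% | 46% | 364 |

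Power is 42% to 61% over this range, and lower beyond it (16% at −10).

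**Step 4. The sign.** Any rewording of 12.5 has to say which direction is good. The first row of the literature table is 31.9 pre-operatively minus 26.0 at last follow-up = 5.9, so a positive entry is a loss of kyphosis. H1 in Section 12.2 (μ_R ≥ OPC − δ) and the assumed 4.0 in Section 12.3 both treat larger as better. The two cannot share one scale as they stand.

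**The case against.** The strongest reply is that the intent is plain. Section 12.5 itself explains success rate as mean thoracic correction, compares it with a mean in degrees, and follows hypotheses and a sample size that are both about a mean. On that reading an exact test against 2.2 exists and loses almost no power, and no cut-off is needed.

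Much of this stands. A reader might infer that the primary analysis cannot be run at all, or that the 80% power or the 173 is wrong. The documents support neither: the mean reading can be run, and the sample size reproduces exactly.

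What the reply does not cure is Section 12.2, which independently defines the endpoint as a rate of subject success. The word is therefore not a single slip in 12.5. Even on the mean reading, 12.5 and 12.3 name different tests.

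A reader might also infer from the sign of the table that the trial is powered to show the Rail worse. The documents do not establish that. They call the quantity a correction and write H1 with larger as better, so they leave the sign unsettled rather than fixing it as a loss. This is a question of direction, not of which test is used.

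**Conclusion.** The inconsistency is real and should be corrected before analysis. The endpoint definition in Section 12.2 and the test in Section 12.5 are wrong as written, and they do not match the hypotheses or the powered analysis.

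The consequence depends on the reading. If a mean was meant, which is the more likely intent, the practical cost is one to two points of power plus a plan that cannot be checked word for word. If a rate was meant, the 80% does not carry over. The 42% to 61% rests on assumed normality and assumed cut-offs and shows only the order of the loss; the plan gives nothing from which to compute the true figure.

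The figures 173, 204 and 80% are correct for the two-sided one-sample t-test with the null at 2.2 and a distance of 1.8 degrees.

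**What to change.** 1. **Section 12.5.** Replace the sentence with, for example: *The mean change in T4–T12 thoracic kyphosis, in degrees, from pre-operative to 24 months will be compared with the literature benchmark by a two-sided one-sample t-test at the 0.05 level, with a 95% confidence interval.* This matches Section 12.3.
2. **Section 12.2.** Replace the rate of subject success with that same mean change.
3. **Sign.** State one convention and apply it to the table, the H0/H1 inequalities, the benchmark, the assumed mean in Section 12.3 and the direction that favours the Rail. If loss is positive, the inequality in 12.2 must be reversed and the margin becomes OPC + δ. Otherwise 12.5 would point the opposite way to the hypotheses.
4. **Responder rate.** If one is kept, make it secondary, with its cut-off and reference rate stated in advance.
5. **Intra-operative exclusions.** Section 8.3 labels these subjects failures and Section 12.4 keeps all enrolled subjects in the ITT set. A failure label has no value in degrees, so 12.5 should say how they enter the mean.

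Three separate points must be settled before the null in 12.5 is fixed:

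- The benchmark of 2.2 against the table's last row, labelled "Weighted Mean Difference and SD", which prints 2.1 (1326.8/639 = 2.08).
- The null of OPC − δ (2.2 − 2 = 0.2) in Section 12.2 against 2.2 in Sections 12.3 and 12.5.
- The non-inferiority and superiority wording in Section 12.2.

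If any of them moves the null, N must be re-derived. With 4.0, SD 8.4 and the same t-test kept, a null of 2.1 needs 156 evaluable subjects and a null of 0.2 needs 41.

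The cost is about a paragraph across Sections 12.2, 12.3 and 12.5 and agreement on the sign and the null. No new data are needed.
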